3.2.1.1 THU Dosing

Weight (kg)	THU (caps/dose)
40-59	2
60-79	3
80-99	4
100-119	5
120-139	6

3.2.1.2 DAC Dosing

					DAC Pills	/week				
Mass (kg)	Total # Pills	wk1 (T;W)	wk2 (T;W)	wk3(T;W)			wk6(T;W)	wk7(T;W)	wk8(T;W)	wk9(T;W
40-49	18	2;1	2;1	none	2;1	2;1	none	2;1	2;1	none
50-59	22	2;2	2;2	none	2;2	2;1	none	2;2	2;1	none
60-69	26	3;2	2;2	none	3;2	2;2	none	2;2	2;2	none
70-79	30	3;2	3;2	none	3;2	3;2	none	3;2	3;2	none
80-89	34	3;3	3;3	none	3;3	3;2	none	3;3	3;2	none
90-99	38	4;3	3;3	none	4;3	3;3	none	3;3	3;3	none
100-109	42	4;3	4;3	none	4;3	4;3	none	4;3	4;3	none
110-119	46	4;4	4;4	none	4;4	4;3	none	4;4	4;3	none
120-129	50	5;4	4;4	none	5;4	4;4	none	4;4	4;4	none
130-139	54	5;5	5;4	none	5;4	5;4	none	5;4	4;4	none
) Ose Level 1:	DAC 2.5 mg/kg	/course								
					DAC Pills/	week				
Mass (kg)	Total # Pills	wk1 (T;W)	wk2 (T;W)	wk3(T;W)			wk6(T;W)	wk7(T;W)	wk8(T;W)	wk9(T;W
40-49	22	2;2	2;2	none	2;2	2;1	none	2;2	2;1	none
50-59	27	3;2	2;2	none	3;2	2;2	none	3;2	2;2	none
60-69	32	3;3	3;3	none	3;3	3;3	none	3;2	3;2	none
70-79	37	4;3	3;3	none	3;3	3;3	none	3;3	3;3	none
80-89	42	4;3	4;3	none	4;3	4;3	none	4;3	4;3	none
90-99	47	4;4	4;4	none	4;4	4;4	none	4;4	4;3	none
100-109	52	5;4	5;4	none	5;4	4;4	none	5;4	4;4	none
110-119	57	5;5	5;4	none	5;5	5;4	none	5;5	5;4	none
120-129	62	6;5	5;5	none	6;5	5;5	none	5;5	5;5	none
130-139	67	6;6	6;5	none	6;6	6;5	none	6;5	5;5	none
Dose Level 2:	DAC 3.0 mg/kg	/course								
					DAC Pills/	week				
Mass (kg)	Total # Pills [#]	wk1 (T;W)	wk2 (T:W)	wk3(T:W)			wk6(T:W)	wk7(T:W)	wk8(T:W)	wk9(T:W
40-49	27	3;2	2;2	none	3;2	2;2	none	3;2	2;2	none
50-59	33	3;3	3;2	none	3;3	3;2	none	3;3	3;2	none
60-69	39	4;3	3;3	none	4;3	3;3	none	4;3	3;3	none
70-79	45	4;4	4;3	none	4;4	4;3	none	4;4	4;3	none
80-89	51	5;4	4;4	none	5;4	4;4	none	5;4	4;4	none
90-99	57	5;5	5;4	none	5;5	5;4	none	5;5	5;4	none
100-109	63	6;5	5;5	none	6;5	5;5	none	6;5	5;5	none
110-119	69	6;6	6;5	none	6;6	6;5	none	6;6	6;5	none
120-129	75	7;6	6;6	none	7;6	6;6	none	7;6	6;6	none
130-139	81	7;7	7;6	none	7;7	7;6	none	7;7	7;6	none

Note: Dose is to be adjusted based on weight changes during the treatment only if patients fall into a different weight category bracket.

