3.1.3 Dose Escalation

The revised dosing regimen selected for this trial is based on pharmacodynamic evidence of systemic hypomethylation without significant systemic toxicities mediated by oral DAC-THU in patients with sickle cell disease in a recent Phase 1 clinical trial (108), as well as experience with DAC-THU/Pembrolizumab in NSCLC (Section 1.2.11.2). The frequency of DAC-THU dosing will increase using a conventional 3+3 Phase I study design attempting to maximize systemic DNMT1 depletion while avoiding Grade 3 or greater systemic toxicities (primarily neutropenia/thrombocytopenia). *Due to the uncertainty regarding cumulative toxicities, no intrapatient escalation will be allowed.*

Dose escalation will proceed as indicated in **Table 7** using three patients per dose level (irrespective of Tumor PD-L1 expression) until DLT within the first 6 weeks (two cycles) of DAC-THU therapy is observed. If one of three patients at any given dose level experiences DLT, up to three additional patients will be treated at this dose level. If only one of six patients exhibit DLT, subsequent patients will be enrolled into the next higher dose level. As soon as two patients at any given dose level develop DLT, no additional patients will be entered at that level. Subsequent patients will be accrued into the preceding dose level; if DLT is observed in less than two of six patients treated at this lower level, this dose will represent maximum tolerated dose (MTD).

Table 7: DAC-THU Dosing Schema for High (50% or Greater) and Low (0-49%) PD-L1
Expression Groups

Dose Level	DAC	DAC	THU	THU	Frequency^
	mg/kg/course	mg/kg/day*	mg/kg/course	mg/kg/day*	wk 1,2,4,5,7,8
-1	2.0	0.17	120	10	T;W
1	2.5	0.21	120	10	T;W
2	3.0	0.25	120	10	T;W
*on days a	administered				
^ T: Tuesd	lay; W: Wednesday				

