3.2.3 CCR Self – Administered Study Drugs Policy

All oral self-administered investigational agents will be properly accounted for, handled, and disposed in accordance with existing federal regulations and principles of Good Clinical Practice. All oral study drugs will be recorded in the patient diary found in **Appendix 2**. This will be used as a memory aide for subjects. The clinical research team will maintain the primary source record.

Subjects should be asked to bring the diary as well as unused study agent and empty containers with them at each study visit. If a subject goes off study while at home, the research nurse will ensure and document the return of the unused oral investigational agents from the participant.

Unused investigational study agents will be disposed and destroyed per CC pharmacy SOPs.

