3.3.5 Dose Modification of DAC-THU

Table 9 lists standard laboratory values that should trigger dose modifications of the investigational drug.

General Adverse Events	Action		
Non-hematological, Grade 1 or 2 (excluding hemorrhage)	 Continue DAC-THU therapy at full dose prescribed. Apply maximum supportive care recommendations. If prolonged duration of Grade 2 adverse event (≥ 7 days) is affecting quality of life, start the next treatment cycle at DL-1. If event persists and continues to affect quality of life for ≥ 7 more days following initial dose reduction, discontinue DAC-THU. 		
Grade 3 ALT and AST	 Hold DAC-THU therapy until recovery to Grade ≤ 1. If ALT and AST resolve to Grade ≤ 1 within 10 days, maintain current dose level. If ALT and AST do NOT resolve to Grade ≤ 1 within 10 days, dose reduce 1 level. If Grade 3 ALT or AST occurs after dose reduction, discontinue DAC-THU. 		

 Table 9: Trigger Values that Result in Dose Modification

General Adverse Events	Action	
Grade 4 ALT and AST	 Hold DAC-THU therapy until recovery to Grade ≤ 1. Resume DAC-THU at DL-1. If Grade 4 toxicities occur after dose reduction, discontinue DAC-THU. 	
Non-hematological, Grade 3 or 4 (excluding ALT, AST, hemorrhage and QT prolongation)	 Apply maximum supportive care recommendations. Hold DAC-THU until recovery to Grade ≤ 1 and resume DAC-THU at the next lower dose level. If symptoms continue to persist at Grade 3 or 4, following dose reduction, discontinue drug. 	
QT prolongation, Grade 3 or 4	 Cardiology consultation will be obtained to determine whether any cardiac functional assessment is warranted or if therapy should be delayed or discontinued. When warranted, ECGs will subsequently be reviewed by the NCI consulting cardiologist. If therapy is continued, dose reduce 1 level for Grade 4 events. If Grade 3 or 4 toxicities occur after dose reduction discontinue DAC-THU. 	
Thrombocytosis	 If platelet count > 500/ mcL but < 1.2M/mcL, continue DAC-THU at current dose. Begin ASA 325mg PO daily. If platelet count 1.2M /mcL or more, hold DAC-THU until platelet count < 1.2 M/mcL, begin ASA 325 mg PO daily and resume DAC-THU at DL-1 if within the first two Cycles of Course 1; or at SAME dose or DL-1 per PI discretion in subsequent cycles. 	
Hemoglobin	• Hgb > 18 g/dL: hold DAC-THU until Hgb WNL. Resume DAC-THU at DL-1.	
Hematological Adverse Events		

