13.1.5 Formulation

Decitabine is manufactured by IriSys LLC (San Diego, CA) and supplied by DCTD as a freeze-dried powder in 20 mL-capacity vials containing DAC 50 mg with 68 mg potassium phosphate, and NaOH. Decitabine will be encapsulated by IriSys LLC under contract with the NIH CC Pharmacy per federal Good Manufacturing Practice guidelines. In this formulation decitabine is supplied as capsules containing 5 mg of decitabine per capsule, in bottles containing 30 capsules, together with a drying agent. The label on the bottles includes the following information: the (i) name of the drug; (ii) quantity of drug per capsule; (iii) date of packaging; (iv) recommended storage temperature; (v) lot number of bulk drug used to generate the capsules

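### The Dose Level 1 decitabine row for 60-69 kg is internally inconsistent: the weekly cells add to 34 capsules, the stated course total is 32.

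*Combined protocol and SAP*

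**What the plan says.** Section 3.2.1.2 tabulates decitabine capsules by weight band for each dose level, with a course total followed by Tuesday;Wednesday counts for each of nine weeks. The Dose Level 1 row for 60-69 kg is "60-69 32 3;3 3;3 none 3;3 3;3 none 3;2 3;2 none". The neighbouring rows are "50-59 27 3;2 2;2 none 3;2 2;2 none 3;2 2;2 none" and "70-79 37 4;3 3;3 none 3;3 3;3 none 3;3 3;3 none".

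Table 7 in Section 3.1.3 gives Dose Level 1 as "1 2.5 0.21 120 10 T;W", that is, 2.5 mg/kg per course and 0.21 mg/kg on each dosing day. Section 13.1.5 gives the strength: "decitabine is supplied as capsules containing 5 mg of decitabine per capsule". Section 3.1.3 continues dosing at a level until "DLT within the first 6 weeks (two cycles) of DAC-THU therapy is observed". Section 3.2.3 (CCR Self-Administered Study Drugs Policy) provides that "All oral study drugs will be recorded in the patient diary" and asks patients to bring back unused drug and empty containers.

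As a separate item, the thrombocytosis row of Table 9 (Section 3.3.5) says "If platelet count > 500/ mcL but < 1.2M/mcL, continue DAC-THU at current dose" and starts daily aspirin in that range.

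**The concern.** A dosing row should give one answer. Here the daily schedule and the course total differ by two capsules, and no visible text says which governs. A patient who takes the weekly cells takes two capsules more than the stated total, so any pill count or diary check against that total will not reconcile.

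The surplus appears to fall in weeks 1, 2, 4 and 5, which are all 3;3. Those weeks lie inside the six-week DLT window, so patients in this band would be assessed for DLT at a higher weight-adjusted dose than patients at the same position in any other Dose Level 1 band.

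Dose Level 1 also matters beyond the first escalation cohort. It is the next lower dose for patients reduced from Dose Level 2, and it could become the MTD. In that case every 60-69 kg patient in the expansion cohorts would use this row in each course.

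**Working it through.** **Inputs.** Weekly cells and totals: Section 3.2.1.2. Dose of 2.5 mg/kg per course on Tuesday and Wednesday of weeks 1, 2, 4, 5, 7 and 8 (12 dosing days): Table 7. Capsule strength of 5 mg: Section 13.1.5. Band midpoint is taken as the lower bound plus 5 kg.

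**1. Row sum.** (3+3)+(3+3)+(3+3)+(3+3)+(3+2)+(3+2) = 34, against a stated 32. Weeks 3, 6 and 9 are marked none and add nothing. The same sum on all 30 rows (three levels, ten bands) reproduces the stated total in 29. This row is the only failure.

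**2. Which number is wrong.** Target capsules = 2.5 × midpoint / 5. For the ten Dose Level 1 bands this gives 22.5, 27.5, 32.5, 37.5, 42.5, 47.5, 52.5, 57.5, 62.5 and 67.5. The stated totals are 22, 27, 32, 37, 42, 47, 52, 57, 62 and 67: the half capsule is dropped every time. So 32 follows the rule and 34 does not.

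**3. Size over a course.** 34 × 5 = 170 mg; 32 × 5 = 160 mg; difference 10 mg, and 10/160 = 6.25%. At 65 kg, 170/65 = 2.62 mg/kg and 160/65 = 2.46 mg/kg, against a target of 2.5. The other nine bands give 2.44-2.48 mg/kg at their midpoints.

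**4. Size in weeks 1-6.**

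| Row | Capsules | mg/kg at band midpoint |
|---|---|---|
| Level 1, 60-69 kg, printed | 24 | 120/65 = 1.85 |
| Level 1, 60-69 kg, corrected | 22 | 110/65 = 1.69 |
| Level 1, other nine bands | 15-46 | 1.64-1.70 |
| Level 2, 60-69 kg | 26 | 130/65 = 2.00 |

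The printed row is 24/22 − 1 = 9.1% above the corrected one and, in capsules, halfway to Dose Level 2. It is also the highest Dose Level 1 row at the lower band edge (120/60 = 2.00 against at most 75/40 = 1.875) and at the upper edge (120/69 = 1.74 against at most 230/139 = 1.65). Section 6.3.2 instead describes a three-week DLT window. On that reading the printed row gives 12 capsules, 60/65 = 0.92 mg/kg, against 0.82-0.89 in the other nine bands.

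**5. Where the surplus sits.** Weeks 1-6 carry 66.7-68.7% of the course in the other nine bands. Taking two capsules from weeks 1-6 gives 22/32 = 68.8%. Taking them from weeks 7-8 gives 24/32 = 75%, which is off the table's pattern.

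**The case against.** The arithmetic is not in dispute; the weight placed on it is.

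Ten-kilogram bands and 5 mg capsules already accept more variation than this error adds. At the correct 32 capsules the band runs from 160/60 = 2.67 to 160/69 = 2.32 mg/kg, a spread of 0.35, whereas the error adds 10/65 = 0.15 at 65 kg. A correctly dosed 40 kg patient receives 1.875 mg/kg in weeks 1-6, more than a 65 kg patient on the printed row. This stands as a limit on consequence. It does not remove the band effect, because it compares different positions within bands; at like positions the printed row is the highest.

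Only the daily cells can be followed as a schedule, since a total assigns no capsules to days. In practice patients would probably take the printed cells, no day would exceed three capsules, and no day would exceed what the band takes at Dose Level 2. That narrows the ambiguity, but it also makes the over-total dose the likely one. The protocol does not explicitly require reconciliation against the total, so that consequence is an inference from the diary and drug-return provisions.

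A misreading when the table was converted from PDF is possible: two cells of 3;2 read as 3;3 would produce exactly this mismatch. With a complete, aligned row and 29 others that reconcile, it is unlikely. A look at the source table would settle it.

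The Table 9 unit is a different kind of error and adds nothing to the weight of this one.

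**Conclusion.** The concern holds. The row contradicts itself by two capsules, and the rounding rule shared by all ten Dose Level 1 totals points to the weekly cells as the error. Followed as printed, it gives 10 mg (6.25%) more per course and two capsules (9.1%) more in the six-week DLT window, as one extra capsule on 2 of 12 dosing days. No patient harm and no changed escalation decision is claimed. It should be fixed because it is an operative instruction at a dose level under evaluation.

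The conclusion rests on the table being as printed. The mg/kg figures rest on 5 mg capsules and, where stated, band midpoints. That the surplus lies in weeks 1-6 is inferred from the pattern of the other rows.

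The Table 9 lower bound is separately a probable unit slip. Eligibility in Section 2.1.1.13 requires at least 100,000 platelets/mcL, so every patient meeting that criterion would already exceed 500/mcL at entry.

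**What to change.** Confirm the row against the source table, keep the total of 32, and change two of the four 3;3 weeks to 3;2. One choice is weeks 2 and 5: 3;3 / 3;2 / none / 3;3 / 3;2 / none / 3;2 / 3;2 / none, which sums to 6+5+6+5+5+5 = 32. This gives 11, 11 and 10 capsules per cycle, the same front-loading as the Dose Level 1 row for 120-129 kg (21, 21, 20). Other pairs among the four weeks also reach 32, so the sponsor should choose.

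Then check dispensing sheets and diaries, and record the dose actually taken by any 60-69 kg patient treated at Dose Level 1. In the same amendment, correct the lower platelet bound in Table 9 (probably 500,000/mcL, for the sponsor to confirm).

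The cost is one table row and one unit in the next amendment, a pharmacy notice and a short look-back. Design and sample size are unaffected.

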Pre-clinical studies in mice and baboons suggested that combining oral THU with oral DAC could address the very poor oral bioavailability and very wide inter-individual variability, creating the rationale for this first-in-man clinical trial of oral THU-DAC (**Figure 13**) (59). Samples for PK analyses were obtained at 0, 2, 4 and 24 hours in 12 of the 15 subjects who received study drug (dictated by venous access). DAC levels were measurable even in subjects receiving the lowest DAC dose of 0.01 mg/kg. A dose-dependent increase in plasma DAC was observed. The highest dose of oral Dec, 0.16 mg/kg, produced DAC plasma concentrations at 2 hours between 39-54 nM. The dose level below this, 0.08 mg/kg, produced concentrations at 2 hours of between 9-21 nM. These concentrations of DAC were in the range predicted to have non-cytotoxic epigenetic therapeutic effects (59), and accordingly, these dose levels were the only ones also associated with clinical pharmacodynamic effects, as described below. The model fit suggested C_{max} was at approximately 1 hour, prior to the 2 hour time-point measured in this study. At all dose levels, by 4 hours, DAC plasma levels had decreased to < 50% of the level measured at 2 hours.

[figure not shown]

Figure 13: Pharmacokinetics (PK) of DAC and oral THU-DAC. A) DAC (Dec in this figure) PK after intravenous (IV), subcutaneous (SQ) and oral (PO) administration to baboons. B) DAC PK in human subjects from this clinical trial. Samples for PK analysis were obtained in 12 of the 15 subjects who received study drug. Stated times are hours after administration of oral Dec, data-points are measured values while curves were fitted by a global fit model using the R package *PKLMfit.R*. The inset shows a close up for hours 0-4, to facilitate comparison to the 4 hour time-frame of the PK studies in baboons. Dec was quantified by a validated LC-MS/MS method. C) Dec AUC estimations in the baboons and in the different cohorts of the human clinical trial (model-dependent AUC estimates *PKLMfit.R*). The objectives with combination with THU were a wider concentration-time profile (that is low Cmax but extended Tmax or t¹/₂) and Dec distribution through CDA rich organs such as the intestines and liver.

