2.3.1 Treatment Assignment Procedures

Cohorts

Number	Name	Description
1	Dose-Escalation	Subjects enrolled to dose escalation cohorts
2	Dose Expansion: NSCLC with high PD-L1	NSCLC subjects with high PD-L1 tumor expression enrolled at the MTD after the MTD is established
3	Dose Expansion: NSCLC with low PD-L1	NSCLC subjects with low PD-L1 tumor expression enrolled at the MTD after MTD is established
4	Dose Expansion: EsC	EsC subjects enrolled at the MTD after MTD is established
5	Dose Expansion: MPM	MPM patients enrolled at the MTD after MTD is established

Arms

Number	Name	Description
1	Dose Escalation	DAC-THU + pembrolizumab at escalating doses
2	Dose Expansion	DAC-THU + pembrolizumab at the dose established in Arm 1

Arm Assignment

Subjects in Cohort 1 will be assigned to Arm 1.

Subjects in Cohort 2, Cohort 3, Cohort 4 and Cohort 5 will be assigned to Arm 2.

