3.3 DOSING DELAYS AND MODIFICATIONS

This study is intended to evaluate the safety and potential efficacy of oral DAC-THU and pembrolizumab as epigenetic immunotherapy in patients with NSCLC, EsC and MPM. The proposed oral DAC dose of ~0.17 mg/kg to be combined with THU ~10 mg/kg administered 60 minutes before oral DAC, is based on non-human primate studies and the Phase 1 clinical trial in SCD which had an identical pharmacologic objective of DAC distribution through tissues with high CDA expression (intestines, liver etc.), and the wide concentration-time profile desired for non-cytotoxic DNMT1-depletion. This dose of DAC administered orally is 10-20% of the FDA-approved dosages administered intravenously and is < 50% of the dose of oral decitabine administered together with another CDA-inhibitor (a THU-analogue) in clinical trials by Astex/Otsuka.

Although it is anticipated that this therapy will be well tolerated at the revised doses, myelosuppression resulting from reprogramming of hematopoietic stem cell differentiation may become dose limiting (50). If dose limiting myelosuppression is observed during the first 2 cycles of Course 1, DAC-THU will be held until toxicities have resolved to Grade 2 or less, and DAC-THU therapy will recommence at the next lower dose, or at the SAME dose if deemed appropriate by the PI, as indicated in the dose escalation schema (**Table 7**). Only one dose reduction will be allowed.

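### The Level 1, 60-69 kg decitabine row states 32 capsules per course but schedules 34, about 12% over target at mid-band in the DLT window

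*Combined protocol and SAP*

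**What the plan says.** Table 7 in Section 3.1.3 sets Dose Level 1 at 2.5 mg/kg of decitabine per course, given in weeks 1, 2, 4, 5, 7 and 8: "1 2.5 0.21 120 10 T;W". Section 13.1.5 supplies the drug as "capsules containing 5 mg of decitabine per capsule". Section 3.2.1.2 turns the target into whole capsules by 10-kg weight band. For Level 1, 60-69 kg, the row is "60-69 32 3;3 3;3 none 3;3 3;3 none 3;2 3;2 none", where the second figure is the course total and each pair is the Tuesday and Wednesday count for one week.

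Three other provisions determine where this row is used:

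- **Escalation** (Section 3.1.3) depends on whether "DLT within the first 6 weeks (two cycles) of DAC-THU therapy is observed". Section 3.1.2 also counts toxicity over the first two cycles. Section 6.3.2 gives a shorter, three-week window.
- **Dose reduction** (Section 3.3): after dose-limiting myelosuppression, "DAC-THU therapy will recommence at the next lower dose", or the same dose if the principal investigator judges it appropriate. Only one reduction is allowed.
- **Expansion** (Section 2.3.1): all expansion cohorts receive "DAC-THU + pembrolizumab at the dose established in Arm 1".

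**The concern.** The row contradicts itself, and the part that patients follow is the part that looks wrong. If 32 is right, the schedule adds two capsules (10 mg) per course, and the likely surplus lies in weeks 1 to 5, when DLTs are counted.

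Three groups would be dosed from this row: Level 1 escalation patients of 60-69 kg; Level 2 patients of that weight after a one-level reduction; and, if Level 1 is declared the MTD, every expansion and Phase II patient of that weight. Escalation uses three to six patients per level and two DLTs close a level, so a single patient dosed above the nominal level can affect the decision. Myelosuppression, the toxicity the plan most expects to limit dosing, is the kind of event extra decitabine could bring on.

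**Working it through.** **Inputs.** Capsule counts from Section 3.2.1.2; targets of 2.0, 2.5 and 3.0 mg/kg/course from Table 7; 5 mg per capsule from Section 13.1.5; band midpoint 64.5 kg. Four of the six dosing weeks (1, 2, 4, 5) fall in the six-week DLT window, so its target is 4/6 of the course target.

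**1. The stated total.** The target reproduces it: 2.5 x 64.5 / 5 = 32.25, or 32 whole capsules. The schedule does not: 6 + 6 + 6 + 6 + 5 + 5 = 34. Summing all 30 rows of the three tables, this is the only mismatch.

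**2. Which figure was intended.** The plan does not say, but the pattern points to 32. Stated Level 1 totals rise by 5 at every band (22, 27, 32, 37, ... 67). The schedule sums for the first five bands are 22, 27, 34, 37 and 42, rising by 5, 7, 3 and 5.

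**3. Course dose.** Scheduled: 34 x 5 / 64.5 = 2.64 mg/kg, which is +5.4% against 2.5. With 32 capsules: 160 / 64.5 = 2.48 mg/kg. The other 29 rows are within 1.1% of their targets at band midpoint.

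**4. DLT-window dose.** Scheduled: 6 + 6 + 6 + 6 = 24 capsules = 120 mg, and 120 / 64.5 = 1.86 mg/kg. Target: 2.5 x 4/6 = 1.667 mg/kg. Excess: 1.860 / 1.667 - 1 = +11.6%. At midpoint the other Level 1 rows run from -0.9% to +2.6%, and all other rows from -0.9% to +4.7%.

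Within the band:

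| Weight | Six-week dose | Against 1.667 mg/kg |
|---|---|---|
| 60 kg | 120 / 60 = 2.00 mg/kg | +20.0% |
| 64.5 kg | 120 / 64.5 = 1.86 mg/kg | +11.6% |
| 69 kg | 120 / 69 = 1.74 mg/kg | +4.3% |

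At 60 kg the six-week dose equals the Level 2 six-week target (3.0 x 4/6 = 2.0 mg/kg).

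**5. Steps between levels, 60-69 kg, DLT-window capsules.**

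| | Level -1 | Level 1 | Level 2 | Step to Level 1 | Step to Level 2 |
|---|---|---|---|---|---|
| As printed | 18 | 24 | 26 | 24/18 = +33% | 26/24 = +8% |
| Corrected (22 capsules) | 18 | 22 | 26 | 22/18 = +22% | 26/22 = +18% |

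The other 18 steps lie between +17% and +25%.

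**6. Level 2 to Level 1 reduction, capsules per course.** As printed: 34/39 - 1 = -12.8%. With 32: 32/39 - 1 = -17.9%. The other nine bands run from -17.3% (67/81) to -18.5% (22/27).

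**7. Secondary point: Table 7's daily figure.** It is the course dose divided by 12 (2.5 / 12 = 0.21), although it is labelled as applying on the days of administration. Whole capsules put the actual Day 1 dose at midpoint 2% to 32% above it at Level 1 (median 13%) and 4% to 35% above it at Level 2 (median 11%).

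**The case against.** **The 12% is a midpoint figure for part of the course.** This is right, and the figure should be quoted that way. Over nine weeks the midpoint excess is 5.4%, and 10-kg bands already give individuals deviations of similar size: a 40-kg patient is 12.5% above target in the DLT window at all three levels. But no correctly summed row reaches +20% at its lower edge, and the others fall at or below target by their upper edge. This row is above target at every weight in the band.

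**The contrast with other rows depends on the window.** Under Section 6.3.2's three weeks, this row is still +11.6% (12 capsules), but some correctly summed rows come close: Level -1, 50-59 kg is 8 x 5 / 54.5 = 0.734 against 0.667, or +10.1%; Level 1, 40-49 kg is 8 x 5 / 44.5 = 0.899 against 0.833, or +7.9%. Two sections support six weeks and one supports three, so the contrast holds on the better-supported reading only. The row error does not depend on the window.

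**The consequence is bounded.** This stands. Even at 60 kg, 34 capsules is 170 / 60 = 2.83 mg/kg, below Level 2's 3.0. Two of the three routes to harm are conditional on Level 1 becoming the MTD or on a Level 2 patient in this band being reduced.

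**The Table 7 point is minor.** Its daily figure can be read as a nominal average, and the exact schedule is printed. That point is about labelling and reporting, and the case for correcting the row does not rest on it.

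**Conclusion.** The concern holds. The row is wrong as written: it states 32 capsules and schedules 34. Following the schedule puts patients of 60-69 kg at Level 1 above target by 5.4% over the course and 11.6% in the six-week DLT window at mid-band (4.3% to 20.0% across the band). It also distorts both escalation steps and weakens the one permitted reduction from Level 2. It does not overturn MTD assignment by level, because dose still rises at each step in every band.

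The sizes assume that the 2.5 mg/kg target is correct, that 32 was the intended total, and that patients take what the weekly cells show. The intended total is an inference from the target and the run of totals, so the sponsor should confirm it. The row should also be checked against the source dosing table, although an isolated transcription fault is unlikely when the other 29 rows agree.

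**What to change.** Once 32 is confirmed, replace the six dosing weeks with 3;3, 3;2, 3;3, 3;2, 3;2, 3;2 (6 + 5 + 6 + 5 + 5 + 5 = 32). This leaves 22 capsules in the DLT window: 110 / 64.5 = 1.71 mg/kg, +2.3%. It follows the alternation already used at Level 2, 50-59 kg: "50-59 33 3;3 3;2 none 3;3 3;2 none 3;3 3;2 none".

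Other 32-capsule schedules are possible, but the two capsules must come out of weeks 1 to 5. Taking them from weeks 7 and 8 corrects the total yet leaves 24 in the DLT window and steps of +33% and +8%. The schedule above also brings the first three weeks to 11 x 5 / 64.5 = 0.853 mg/kg against 0.833, or +2.3%, so it works under either DLT window.

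If anyone in this band has already been dosed at Level 1, report the capsules actually taken.

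As a lesser change, label Table 7's daily decitabine figure as the average over 12 dosing days, and report each PK profile with the milligrams taken that day. Dose-normalised exposure could be added, but it assumes proportionality. The sickle cell data in Section 1.2.9 leave that uncertain: 9-21 nM at 0.08 mg/kg, whereas "0.16 mg/kg, produced DAC plasma concentrations at 2 hours between 39-54 nM". That is limited evidence, from a single time point.

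The cost is one table row, one column label and one reporting sentence, with no new visits. Oral doses are already to be recorded in the patient diary, with a primary source record kept by the research team; confirm that one of these captures the number of capsules.
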